1. Institutional Review Board/Independent Ethics Committee-approved written informed consent and privacy language as per national regulations (e.g., Health Insurance Portability and Accountability Act authorization for US study sites) must be obtained from the subject or legally authorized representative prior to any study-related procedures (including withdrawal of prohibited medication, if applicable).
2. Subject is considered an adult according to local regulation at the time of signing the informed consent form.
3. Subject diagnosed with R/R AML or R/R higher risk MDS is defined as:
 - R/R AML
 - Morphologically documented primary or secondary AML by the WHO criteria (2016),
AND
 - Refractory to at least 2 cycles of induction chemotherapy/not a candidate for re-induction OR relapsed after achieving remission with a prior therapy,
AND
 - Received all standard therapies including targeted therapies (unless the therapy is contraindicated or intolerable) which are known to provide clinical benefit in the opinion of the treating investigator,
AND
 - Received salvage therapy OR is not a candidate for salvage therapy

- R/R Higher Risk MDS
 - Has MDS by the WHO criteria (2016),
AND
 - Either relapsed after achieving remission or refractory to standard therapies, including ≥ 4 cycles of hypomethylating agents (unless the therapy is contraindicated or intolerable),
AND
 - Is classified as higher risk MDS with a score of > 3.5 by Revised IPSS-R in MDS

4. Subject has an Eastern Cooperative Oncology Group performance status of ≤ 2 .
5. Subject must meet the following criteria as indicated on the clinical laboratory tests during screening period:
 - Serum aspartate aminotransferase and alanine aminotransferase $\leq 2.5 \times$ upper limit of normal (ULN)
 - Serum total bilirubin $\leq 1.5 \times$ ULN
 - Serum creatinine $\leq 1.5 \times$ ULN or an estimated glomerular filtration rate of > 50 mL/min as calculated by the Modification of Diet in Renal Disease equation.
 - Platelets $\geq 50,000/\mu\text{L}$ at cycle 1 day 1 (C1D1) in the dose escalation cohorts only
6. Subject has a life expectancy of ≥ 12 weeks at the time of screening in the opinion of the investigator.
7. Subjects with AML must have peripheral blood absolute blast count of $< 20,000/\mu\text{L}$ at C1D1.
Note: Blast count can be controlled by hydroxyurea during screening period.

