8. Female subject is not pregnant [see Appendix 12.3 Contraception Requirements] and at least 1 of the following conditions apply:
 - Not a woman of childbearing potential (WOCBP) [see Appendix 12.3 Contraception Requirements]
 - WOCBP who agrees to follow the contraceptive guidance [see Appendix 12.3 Contraception Requirements] from the time of informed consent through at least 180 days after final study treatment administration.
9. Female subject must agree not to breastfeed starting at screening and throughout the study period and for 180 days after the final study treatment administration.
10. Female subject must not donate ova starting at first dose of IP and throughout the study period and for 180 days after final study treatment administration.
11. Male subject with female partner(s) of childbearing potential (including breastfeeding partner) must agree to use contraception [see Appendix 12.3 Contraception Requirements] throughout the treatment period and for 180 days after final study treatment administration.
12. Male subject must not donate sperm during the treatment period and for 180 days after the final study treatment administration.
13. Male subject with pregnant partner(s) must agree to remain abstinent or use a condom for the duration of the pregnancy throughout the study period and for 180 days after final study treatment administration.
14. Subject agrees not to participate in another interventional study while receiving study treatment in the present study.

Waivers to the inclusion criteria will **NOT** be allowed.

Exclusion Criteria:

Subject will be excluded from participation in the study if any of the following apply:

1. Subject was diagnosed with acute promyelocytic leukemia.
2. Subject has breakpoint cluster region-Abelson-positive leukemia (BCR-ABL).
3. Subject has persistent non-hematological toxicities of \geq grade 2 (National Cancer Institute's Common Terminology Criteria for Adverse Events [NCI-CTCAE], version 5.0), with symptoms and objective findings from prior AML or MDS treatment (including chemotherapy, kinase inhibitors, immunotherapy, experimental agents, radiation or surgery).
4. Subject has received any of the following therapies:
 - Systemic immunomodulators or immunosuppressive drugs including steroids \leq 28 days prior to C1D1 (steroids can be used if not intended for treatment of AML or MDS; steroids for AML/MDS related symptoms can be used at low doses [less than 10 mg/day dexamethasone])

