 - Cytotoxic agents (except hydroxyurea given for controlling blast cells) \leq 28 days prior to C1D1
 - Investigational products for the treatment of AML or MDS within 5 half-lives prior to screening visit
 - Hematopoietic stem cell transplant (HSCT)
 - Radiation therapy \leq 28 days prior to C1D1
5. Subject has clinically active nervous system leukemia, per the investigator's judgment.
6. Subject has active or prior documented autoimmune or inflammatory disorders requiring systemic treatment.
7. Subject has ongoing, untreated malignancy with the exception of the following:
 - Subjects with treated non-melanoma skin cancer, in situ carcinoma or cervical intraepithelial neoplasia, regardless of the disease-free duration, are eligible for this study if definitive treatment for the condition has been completed.
 - Subjects with organ-confined prostate cancer with no evidence of recurrent or progressive disease are eligible if hormonal therapy has been initiated or the malignancy has been surgically removed or treated with definitive radiotherapy.
8. Subject with left ventricular ejection fraction of $< 45\%$ on echocardiogram or multigated acquisition scan (MUGA) performed within 28 days of screening.
9. Subject has laboratory abnormalities or clinical evidence of disseminated intravascular coagulation, or ongoing history of coagulation disorder manifested by bleeding or clotting.
10. Subject has an active uncontrolled infection.
11. Subject is known to have human immunodeficiency virus infection.
12. Subject has active hepatitis B or C or other active hepatic disorder.
13. Subject has any condition, which in the investigator's opinion, makes the subject unsuitable for study participation.
14. Subject has a known or suspected hypersensitivity to bovine-derived protein or has suspected hypersensitivity to any ingredients of ASP7517.
15. Subject is eligible for HSCT.

Waivers to the exclusion criteria will **NOT** be allowed.

Investigational Product(s):

ASP7517 injection 1×10^7 cells/mL, 2.5 mL/vial for intravenous infusion.

Dose(s):

Phase 1 (Dose Escalation)

Starting dose of ASP7517 is 1×10^6 cells/dose, with escalation doses of 1×10^7 and 1×10^8 cells/dose.

Subjects will receive 2 single doses of ASP7517 on C1D1 and cycle 2 day 1 (C2D1).

Phase 2 (Dose Expansion)

Subjects will receive 1 dose of ASP7517 on day 1 of each 28-day cycle at RP2D or MTD as established by phase 1 for up to 6 doses total during the expansion phase.

Mode(s) of Administration:

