AE: adverse event; CT: computed tomography; C: cycle; D: day; C1D1: cycle 1 day 1; ECG: electrocardiogram; ECHO: echocardiogram; ECOG: Eastern Cooperative Oncology Group; ELISpot: enzyme-linked immunospot; EoT: end-of-treatment; HLA: human leukocyte antigen; ICF: informed consent form; INR: international normalization ratio; IRT: interactive response technology; MUGA: multigated acquisition scan; Obs: observation; PGx: pharmacogenomics; PT: prothrombin time; SAE: serious adverse event; WOCBP: women of childbearing potential; WT1: Wilms' tumor 1 protein.

a. Obtained predose.

b. Obtained predose and postdose (including flushing) (vital signs: hourly [± 10 minute window] for up to 4 hours postdose; ECG: 1 to 2 hours postdose) on C1D1 and C2D1.

c. Height measurement performed only at screening. Weight measurement should be performed at screening and day 1 of each cycle.

Footnotes continued on next page

- d. Includes medications taken within 28 days prior to C1D1.
- e. WOCBP must have a negative serum or urine pregnancy test (minimum sensitivity 25 IU/L or equivalent units of human chorionic gonadotropin) within 72 hours prior to the start of study treatment.
- f. The 12-lead ECGs will be recorded in triplicate (at least 2 minutes apart per time point) and transmitted electronically for central reading.
- g. Laboratory samples will be analyzed by the institution's local laboratory. However, sample results must also be submitted for centralized data entry. Laboratory tests and/or ECG can be repeated during screening period.
- h. Laboratory samples will be analyzed by the institution's local laboratory and results will be submitted for centralized data entry.
- i. Chest X-ray (or CT of chest) does not need to be repeated if performed within 2 weeks prior to start of screening.
- j. MUGA scans or ECHO (per standard of care) performed at screening or within 28 days prior to screening will be accepted.
- k. Screening samples may be collected up to 28 days prior to C1D1. End of treatment bone marrow sample does not need to be repeated if collected within 2 weeks of the last disease assessment. Samples must be submitted to a central laboratory for analysis. If bone marrow aspirate is unobtainable (e.g., dry tap), an additional ethylenediaminetetraacetic acid tube of whole blood should be collected instead. Bone marrow aspirate is required, and bone marrow biopsy is preferred. In case of inadequate aspirate, bone marrow biopsy is required.

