7.2 Safety Assessments

Study procedures and their timing are summarized in the Schedules of Assessments [[Table 1](#) and [Table 2](#)]. Protocol waivers or exemptions are not allowed.

Procedures conducted as part of a subject's routine clinical management (i.e., standard of care) obtained before signing the ICF may be utilized for screening or baseline purposes, provided the procedures met the protocol-specified criteria and were performed within the timeframe, as defined in the Schedules of Assessments [[Table 1](#) and [Table 2](#)].

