9 STATISTICAL METHODOLOGY

A statistical analysis plan (SAP) will be written to provide details of the analysis, along with specifications for tables, listings and figures to be produced. The SAP will be finalized before the database soft-lock at the latest. Changes from the planned analyses in the final SAP that impact the statistical analyses will be justified in the clinical study report (CSR).

In general, all data will be summarized by dose level and overall with descriptive statistics for continuous endpoints, and frequency and percentage for categorical endpoints, unless otherwise specified. Percentages by categories will be based on the number of subjects with no missing data (i.e., will add up to 100%). Kaplan-Meier estimates will be provided for time-to-event endpoints. Separate data displays will be produced for each phase of the study. For phase 1 dose escalation, all data will be summarized by dose level and overall, unless otherwise specified. For phase 2 dose expansion, all data will be summarized by disease group, dose level and overall, unless otherwise specified.

Baseline will be defined as the last nonmissing observation on or prior to first administration of IP, unless otherwise specified.

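### Exclusion 4 sets no interval for approved targeted AML/MDS drugs and the baseline marrow may predate their last dose, so a remission due to the earlier drug can count as an ASP7517 response, mainly in AML

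*Protocol*

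**What the plan says.** Exclusion criterion 4 (protocol 1.1, repeated in 5.2) bars prior stem cell transplant and sets intervals for four kinds of prior treatment:

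- "Systemic immunomodulators or immunosuppressive drugs including steroids": 28 days before C1D1, with stated exceptions for steroids.
- "Cytotoxic agents (except hydroxyurea given for controlling blast cells"): 28 days before C1D1.
- "Investigational products for the treatment of AML or MDS within 5 half-lives prior to screening visit".
- Radiation: 28 days before C1D1.

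Exclusion criterion 3, on residual toxicity, describes prior treatment more fully: "including chemotherapy, kinase inhibitors, immunotherapy, experimental agents, radiation or surgery". Kinase inhibitors stand there as a class apart from chemotherapy and experimental agents. For AML, inclusion criterion 3 requires that the subject "Received all standard therapies including targeted therapies (unless the therapy is contraindicated or intolerable"), and SAP 6.2.6 tabulates prior tyrosine kinase inhibitor use.

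On the baseline marrow, Table 1 footnote k and Table 2 footnote j both say: "Screening samples may be collected up to 28 days prior to C1D1". Protocol 5.4.1 keeps the same 28 days on rescreening. Protocol 7.2 allows routine-care procedures "obtained before signing the ICF may be utilized for screening or baseline purposes". Protocol 9 states: "Baseline will be defined as the last nonmissing observation on or prior to first administration of IP, unless otherwise specified". None of these places requires the marrow to follow the last dose of prior therapy.

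**The concern.** The phase 2 primary endpoint is a single-arm response rate judged against a fixed inefficacious rate: 15% CRc in AML, and 12% CR + BM CR + PR in MDS. There is no control arm in which a carry-over response would also appear, so each one counts toward the success threshold.

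As written, the plan permits this sequence in AML. A marrow on day -28 shows active disease while the subject is taking an approved kinase inhibitor. The drug continues for some time, ASP7517 starts on C1D1, and the C2D1 marrow, about 56 days (28 + 28) after the baseline one, shows remission. That subject is a CRc, and nothing in the data rules out that the remission began before C1D1.

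At stake is the stated control of the type I error at 0.10.

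**Working it through.** **Step 1. Is the drug class covered elsewhere?**

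- Exclusion 4: an approved kinase inhibitor is not investigational. Exclusion 3 lists it separately from chemotherapy, so it does not fall naturally under cytotoxic agents.
- Protocol 6.5 and 12.6.3: other AML/MDS treatment is prohibited during the study. No interval before it is set.
- Protocol 7.1.1.1 and SAP 5.1.1: AML CR, CRp and CRi are judged on post-baseline findings, with no comparison with baseline. An old marrow therefore matters as missing proof of active disease at C1D1.
- Protocol 7.1.1.2: MDS marrow CR and PR need a blast fall of at least 50% from pretreatment, so an old marrow enters the calculation directly.
- Protocol 9.4.1.2 leaves sensitivity analyses to the SAP. SAP 6.4 offers the RAS and investigator-reported response; neither concerns recent prior therapy.

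**Step 2. Reproduce the plan's figure.** Inputs (protocol 9.1 and 9.4.1.3): stages of 12 + 20 + 20.

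| | p0 / p1 | Stop at 12 if | Stop at 32 if | Efficacious at 52 if |
|---|---|---|---|---|
| AML | 0.15 / 0.30 | ≤ 1 | ≤ 5 | ≥ 12 |
| MDS | 0.12 / 0.25 | 0 | ≤ 4 | ≥ 10 |

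Let X1, X2 and X3 be the responses in the three stages, independent binomials with sizes 12, 20 and 20 and probability p. With stopping bounds b1 and b2 and success threshold r, treated as binding:

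P(efficacious) = Σ P(X1 = x) P(X2 = y) P(X3 = w), over x > b1, x + y > b2 and x + y + w ≥ r.

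- AML: type I error 0.0667, power 0.829.
- MDS: type I error 0.0781, power 0.835.

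Both agree with the stated power of about 0.83 and the 0.10 limit.

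**Step 3. Add carry-over (illustration only).** Suppose a share s of subjects respond only because of the earlier drug and the rest respond at p0. Then p = s + (1 − s) × p0. For AML at s = 2%: 0.02 + 0.98 × 0.15 = 0.167. For MDS at s = 2%: 0.02 + 0.98 × 0.12 = 0.1376.

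| s | AML: p | AML: P(efficacious) | MDS: p | MDS: P(efficacious) |
|---|---|---|---|---|
| 0 | 0.150 | 0.067 | 0.120 | 0.078 |
| 0.5% | 0.154 | 0.079 | 0.124 | 0.094 |
| 1% | 0.1585 | 0.092 | 0.1288 | 0.112 |
| 2% | 0.167 | 0.123 | 0.1376 | 0.153 |
| 3% | 0.1755 | 0.160 | 0.1464 | 0.201 |

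The 0.10 limit is passed at s of about 1.3% in AML and 0.7% in MDS. A share of 1/52 (1.9%) gives 0.121 and 0.150.

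SAP 6.7 gives the AML bound at 32 subjects as ≤ 6 rather than ≤ 5. With 6, the AML values at s = 0, 1, 2 and 3% are 0.059, 0.082, 0.110 and 0.144, so the pattern is the same.

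**The case against.** The best reply is that carry-over is unlikely. Subjects must be relapsed or refractory, and for AML must have had all standard therapies unless contraindicated or intolerable, so a late remission on a drug already received should be uncommon. If 10% of subjects came straight off such a drug and 5% of those remitted, s would be 0.10 × 0.05 = 0.5%, and both error rates would stay under 0.10. There is also later disease information than a day -28 marrow: a disease assessment and central blood sample at screening, and predose hematology with blast count at C1D1. This stands as a limit on the likely size. It does not close the gap. A drug stopped for intolerance, or shortly before consent, is still allowed, and blood counts do not exclude marrow remission.

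The MDS side is weaker, and this stands in full. CR, PR and marrow CR must each hold for at least 4 weeks while other MDS therapy is prohibited. The targeted-therapy requirement appears only in the AML criterion. The MDS criterion names hypomethylating agents, and the protocol does not say whether those count as cytotoxic. No approved MDS drug is shown to fall in the gap.

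Three stronger readings are tempting, and the documents do not support them:

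- A reader might infer that residual toxicity of the earlier drug will be mistaken for a DLT. Exclusion 3 bars persistent non-hematological toxicity of grade 2 or higher from prior treatment, kinase inhibitors included. A DLT must also be judged related to the product and be confirmed by the DESC.
- A reader might infer that the rule works differently in Japan, the US and China, because a drug may be approved in one and investigational in another. Nothing in the documents shows this happening.
- A reader might take one row of the table, such as 3%, as the expected bias. No carry-over rate is given, so no row is an estimate.

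**Conclusion.** The gap is real on the text, and the plan as written can credit ASP7517 with a remission produced by an approved drug taken shortly before it. The exposure is mainly in AML.

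The size is unknown. What can be said is that the margin is thin: with the protocol boundaries, an AML carry-over share between 1% and 2% takes the false-positive rate from 0.067 past the stated 0.10. The MDS margin is thinner still, but carry-over there is less plausible. These figures assume binding futility stops, independent subjects, and an inactive product whose remaining subjects respond at exactly 15% or 12%.

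This is a worthwhile and cheap improvement. It is not evidence that the type I error is in fact lost.

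**What to change.** 1. **SAP 6.4.1.** Add a sensitivity analysis of the primary response rate that counts as non-responders those responders whose baseline marrow predates the last dose of prior AML/MDS therapy, hydroxyurea excepted. List all responders by time from last prior AML/MDS dose to C1D1. The data appear to be in hand: SAP 6.2.6 covers prior therapy, and footnote d of Tables 1 and 2 records medication in the 28 days before C1D1, which matches the oldest allowed marrow. Cost: one table and one listing. This also serves subjects already enrolled.
2. **Table 1 footnote k and Table 2 footnote j.** Require the baseline marrow used for response to be taken after the last dose of prior AML/MDS therapy, hydroxyurea excepted. Cost: a wording change, and a later screening marrow for some subjects.
3. **Protocol 1.1 and 5.2.** Reconcile exclusion 4 with exclusion 3 and inclusion 3 by stating how it applies to approved targeted agents, and whether hypomethylating agents count as cytotoxic. Whether there should be an interval, and how long, is the sponsor's clinical decision.

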1.2 Study Schema

Figure 1 Study Schema

Doses: 1×10^6 , 1×10^7 , 1×10^8 cells/dose

[figure not shown]
Dosing frequency:

Phase 1 (Dose Escalation): Subjects will receive 2 single doses of ASP7517 on day 1 of each 28 -day cycle.

Phase 2 (Dose Expansion): Subjects will receive 1 dose of ASP7517 on day 1 of each 28-day cycle at RP2D or MTD as established by phase 1 for up to 6 doses total during the expansion phase.

AML: acute myeloid leukemia; BOP2: Bayesian optimal phase 2; DLT: dose limiting toxicity; MDS: myelodysplastic syndrome; MTD: maximum tolerated dose; subj.: subjects.

Figure 2 Flow Chart

IV: intravenous; mos: months; PI: principal investigator; Q3: every 3.

1.3 Schedules of Assessments

Table 1 Schedule of Assessments – Phase 1 (Dose Escalation)

Assessments	Screening Period	Treatment Period																				End of Treatment ^p	Post-Treatment Period		Survival Follow-up Period ^t				
		Cycle 1							Cycle 2							Obs Period 1	Obs Period 2												
		Hospitalization Days 1 to 7 during phase 1							1	2	3	4	5	6	7	8	11	15	18 22 25	1	2	3	4	5	6	7	8	15	22
Visit Days	-14 to -1	1	2	3	4	5	6	7	8	11	15	18 22 25	1	2	3	4	5	6	7	8	15	22	Every 2 weeks for up to 12 weeks or until 1 post-treatment discontinuation criterion is met	Every 4 weeks or until 1 post-treatment discontinuation criterion is met	Every 3 months				
Window(days)		0	0	0	0	0	0	0	± 1	± 1	± 1	± 1	± 1	± 1	± 1	0	0	0	0	0	0	0	0	0		0	0	0	
Signed ICF	X																												
Medical and Disease History	X																												
Disease Assessment	X																X												
Physical Examination ^c	X	X ^a	X	X	X	X	X	X	X	X	X	X	X	X	X	X ^a	X	X	X	X	X	X	X	X		X	X	X ^q	
Vital Signs	X	X ^b	X	X					X	X	X	X	X	X	X	X ^b	X	X						X		X	X	X ^q	
ECOG Performance	X	X ^a	X	X					X	X	X	X	X	X	X	X ^a	X	X						X		X	X	X ^q	
Prior and Concomitant Medications	X ^d	X	X		X				X	X	X	X	X	X	X	X	X	X						X		X	X	X	
Pregnancy Test for WOCBP	X ^e	X ^a														X ^a												X	
12-Lead ECG ^f	X ^g	X ^b														X ^b												X	
Clinical Laboratory Tests (chemistry, hematology, urinalysis) ^h	X ^g	X ^a	X	X	X	X	X	X	X	X	X	X	X	X	X ^a	X	X	X	X	X	X	X	X	X	X	X ^q			
Coagulation Profile (PT/INR, D-dimer, fibrinogen) ^h	X ^g	X ^a	X	X	X	X	X	X	X	X	X	X	X	X	X ^a	X	X	X	X	X	X	X	X	X	X	X ^q			
Table continued on next page																													

Reference Table 3:
Schedule of
Post-Treatment Period
Assessments

Assessments	Screening Period	Treatment Period																				End of Treatment ^p	Post-Treatment Period		Survival Follow-up Period ^t	
		Cycle 1							Cycle 2														Obs Period 1	Obs Period 2		
	-14 to -1	Hospitalization Days 1 to 7 during phase 1							8	11	15	18 22 25	1	2	3	4	5	6	7	8	15	22	Every 2 weeks for up to 12 weeks or until 1 post-treatment discontinuation criterion is met	Every 4 weeks or until 1 post-treatment discontinuation criterion is met	Every 3 months	
Visit Days	-14 to -1	1	2	3	4	5	6	7	8	11	15	18 22 25	1	2	3	4	5	6	7	8	15	22				
Window(days)		0	0	0	0	0	0	0	±1	±1	±1	±1	+3	0	0	0	0	0	0	0	±1	±1	±1	+7	±3	
Chest X-ray (or CT of chest)	X ⁱ																							Reference Table 3: Schedule of Post-Treatment Period Assessments		
MUGA or ECHO	X ^j																									
Bone Marrow Aspiration and/or Biopsy ^k	X ^k												X ^{a,k}										X ^k			
Blood Sample for Disease Assessment ^l	X												X										X			
AE/SAE Assessment	X	X	X	X	X	X	X	X	X	X	X	X	X	X	X	X	X	X	X	X	X	X				
Pharmacokinetic: Blood Sample for Cell Kinetics		See Table 5 for detailed sample time points																								
PGx		X ^m																						Reference Table 3: Schedule of Post-Treatment Period Assessments		
Blood Sample for WT1 Expression		X ^a											X ^a										X ^q			
Blood Sample for Mutational Profiling		X ^a																					X ^q			
Blood Sample for Immune Response Biomarker (ELISpot)		X ^a						X		X		X ^a							X	X		X ^q				
Buccal Swab for HLA Typing		X ^a																								

Table continued on next page

Assessments	Screening Period	Treatment Period																				End of Treatment ^p	Post-Treatment Period		Survival Follow-up Period ^t	
		Cycle 1							Cycle 2														Obs Period 1	Obs Period 2		
		Hospitalization Days 1 to 7 during phase 1							8	11	15	18 22 25	1	2	3	4	5	6	7	8	15	22	Every 2 weeks for up to 12 weeks or until 1 post-treatment discontinuation criterion is met	Every 4 weeks or until 1 post-treatment discontinuation criterion is met		
Visit Days	-14 to -1	1	2	3	4	5	6	7	8	11	15	18 22 25	1	2	3	4	5	6	7	8	15	22	Every 2 weeks for up to 12 weeks or until 1 post-treatment discontinuation criterion is met	Every 4 weeks or until 1 post-treatment discontinuation criterion is met	Every 3 months	
Window(days)		0	0	0	0	0	0	0	±1	±1	±1	±1	+3	0	0	0	0	0	0	0	±1	±1	±1	+7		±3
Blood Sample for Immune Response Biomarker (Tetramer)		X ^a										X		X ^a									X		X ^q	Reference Table 3: Schedule of Post-Treatment Period Assessments
Blood Sample for Immune Cell Phenotyping		X ^a							X		X		X ^a									X	X		X ^q	
Blood Sample for Cytokines		X ^a	X	X				X		X		X ^a	X		X						X	X		X ^q		
Blood Sample for Anti-HLA Antibody		X ^a																				X		X		
IRT Transaction Required	X	X ⁿ										X												X		
ASP7517 Dosing at the Clinic		X ^o										X ^o														
Survival Follow-up ^r																									X	

AE: adverse event; CT: computed tomography; C: cycle; D: day; C1D1: cycle 1 day 1; ECG: electrocardiogram; ECHO: echocardiogram; ECOG: Eastern Cooperative Oncology Group; ELISpot: enzyme-linked immunospot; EoT: end-of-treatment; HLA: human leukocyte antigen; ICF: informed consent form; INR: international normalization ratio; IRT: interactive response technology; MUGA: multigated acquisition scan; Obs: observation; PGx: pharmacogenomics; PT: prothrombin time; SAE: serious adverse event; WOCBP: women of childbearing potential; WT1: Wilms' tumor 1 protein.

a. Obtained predose.

b. Obtained predose and postdose (including flushing) (vital signs: hourly [± 10 minute window] for up to 4 hours postdose; ECG: 1 to 2 hours postdose) on C1D1 and C2D1.

c. Height measurement performed only at screening. Weight measurement should be performed at screening and day 1 of each cycle.

Footnotes continued on next page

- d. Includes medications taken within 28 days prior to C1D1.
- e. WOCBP must have a negative serum or urine pregnancy test (minimum sensitivity 25 IU/L or equivalent units of human chorionic gonadotropin) within 72 hours prior to the start of study treatment.
- f. The 12-lead ECGs will be recorded in triplicate (at least 2 minutes apart per time point) and transmitted electronically for central reading.
- g. Laboratory samples will be analyzed by the institution's local laboratory. However, sample results must also be submitted for centralized data entry. Laboratory tests and/or ECG can be repeated during screening period.
- h. Laboratory samples will be analyzed by the institution's local laboratory and results will be submitted for centralized data entry.
- i. Chest X-ray (or CT of chest) does not need to be repeated if performed within 2 weeks prior to start of screening.
- j. MUGA scans or ECHO (per standard of care) performed at screening or within 28 days prior to screening will be accepted.
- k. Screening samples may be collected up to 28 days prior to C1D1. End of treatment bone marrow sample does not need to be repeated if collected within 2 weeks of the last disease assessment. Samples must be submitted to a central laboratory for analysis. If bone marrow aspirate is unobtainable (e.g., dry tap), an additional ethylenediaminetetraacetic acid tube of whole blood should be collected instead. Bone marrow aspirate is required, and bone marrow biopsy is preferred. In case of inadequate aspirate, bone marrow biopsy is required.
- l. Samples must be submitted to a central laboratory for analysis.
- m. Whole blood and buccal swab for optional PGx study may be collected at C1D1 prior to first investigational product administration.
- n. Subject enrollment in the study will be conducted via IRT transaction.
- o. After dosing of ASP7517, subjects must be observed for safety for a minimum 4 hours. The safety observation will consist of hourly vital signs and AE observations. If new AEs are observed that are \geq grade 3 during this time, subjects should continue to be observed at the investigator's discretion.
- p. The EoT visit will occur within 7 days of the principal investigator decision to discontinue the subject for treatment or prior to the initiation of new anticancer treatment, whichever occurs first. If a subject is completing all visits in the last treatment cycle, the EoT visit will be within 7 days from the last planned visit.
- q. Assessment does not need to be repeated if collected at a regularly scheduled visit within 3 days of EoT visit.
- r. Telephone contact for survival status and subsequent anti-cancer treatments and outcomes.

Table 2 Schedule of Assessments – Phase 2 (Dose Expansion)

Assessments	Screening Period	Treatment Period														End of Treatment ^a	Post-Treatment Period		Survival Follow-up Period
	Screening	Cycle 1				Cycle 2				Cycles 3 - 4 ^r		Cycles 5 - 6 ^s		Observation Period 1	Observation Period 2	Survival Follow-up			
Visit Days	Days -14 to -1	D1	D2	D8	D15	D22	D1	D2	D8	D15	D22	D1	D15	D1	D15	Every 2 weeks for up to 12 weeks or until 1 post-treatment discontinuation criterion is met	Every 4 weeks or until 1 post-treatment discontinuation criterion is met	Every 3 months	
Window(days)		0	± 1	± 1	± 1	+ 3	0	± 1	± 1	± 1	+ 3	± 1	+ 3	± 1	± 1	+ 7		± 3	
Signed ICF	X																		
Medical and Disease History	X																		
Disease Assessment ^t	X						X					X		X		X			
Physical Examination ^c	X	X ^a	X	X	X	X	X ^a	X	X	X	X	X ^a	X	X ^a	X	X ^p			
Vital Signs	X	X ^b	X	X	X	X	X ^b	X	X	X	X	X ^b	X	X ^b	X	X ^p			
ECOG Performance	X	X ^a	X	X	X	X	X ^a	X	X	X	X	X ^a	X	X ^a	X	X ^p			
Prior and Concomitant Medications	X ^d	X	X	X	X	X	X	X	X	X	X	X	X	X	X	X			
Pregnancy Test for WOCBP	X ^e	X ^a					X ^a					X ^a		X ^a		X			
12-Lead ECG ^f	X ^g	X ^b					X ^b					X ^b		X ^b		X			
Clinical Laboratory Tests (chemistry, hematology, urinalysis)	X ^g	X ^a	X	X	X	X	X ^a	X	X	X	X	X ^a	X	X ^a	X	X ^p			
Coagulation Profile (PT/INR, D-dimer, fibrinogen)	X ^g	X ^a	X	X	X	X	X ^a	X	X	X	X	X ^a	X	X ^a	X	X ^p			

Table continued on next page

Reference [Table 3: Schedule of Post-Treatment Period Assessments](#)

Assessments	Screening Period	Treatment Period														End of Treatment ^o	Post-Treatment Period		Survival Follow-up Period	
	Screening	Cycle 1				Cycle 2				Cycles 3 - 4 ^r		Cycles 5 - 6 ^s		Observation Period 1	Observation Period 2		Survival Follow-up			
	Visit Days	Days -14 to -1	D1	D2	D8	D15	D22	D1	D2	D8	D15	D22	D1	D15	D1	D15	Every 2 weeks for up to 12 weeks or until 1 post-treatment discontinuation criterion is met	Every 4 weeks or until 1 post-treatment discontinuation criterion is met	Every 3 months	
Window(days)		0	± 1	± 1	± 1	+ 3	0	± 1	± 1	± 1	+ 3	± 1	+ 3	± 1	+ 7			± 3		
Chest X-ray (or CT of chest)	X ^h															Reference Table 3: Schedule of Post-Treatment Period Assessments				
MUGA or ECHO	X ⁱ																			
Bone Marrow Aspiration and/or Biopsy ^j	X ^j						X ^{a,j}					X ^{a,j}		X ^{a,j}						
Blood Sample for Disease Assessment ^k	X						X				X		X		X					
AE/SAE Assessment	X	X	X	X	X	X	X	X	X	X	X	X	X	X	X					
Pharmacokinetic: Blood Sample for Cell Kinetics		See Table 5 for detailed sample time points																Reference Table 3: Schedule of Post-Treatment Period Assessments		
PGx	X ^l																			
Blood Sample for WT1 Expression	X ^a					X ^a					X ^a		X ^a		X ^p					
Blood Sample for Mutational Profiling	X ^a														X ^p					
Blood Sample for Immune Response Biomarker (ELISpot)	X ^a		X	X		X ^a		X	X		X ^a	X	X ^a	X	X ^p					
Buccal Swab for HLA Typing	X ^a																			

Table continued on next page

Assessments	Screening Period	Treatment Period												End of Treatment ^a	Post-Treatment Period		Survival Follow-up Period	
	Screening	Cycle 1				Cycle 2				Cycles 3 - 4 ^r		Cycles 5 - 6 ^s			Observation Period 1	Observation Period 2	Survival Follow-up	
	Visit Days	Days -14 to -1	D1	D2	D8	D15	D22	D1	D2	D8	D15	D22	D1	D15	D1	D15		
Window(days)		0	± 1	± 1	± 1	+ 3	0	± 1	± 1	± 1	+ 3	± 1	+ 3	± 1	± 1	+ 7		± 3
Blood Sample for Immune Response Biomarker (Tetramer)		X ^a			X		X ^a			X		X ^a	X	X ^a	X	X ^p	Reference Table 3: Schedule of Post-Treatment Period Assessments	
Blood Sample for Immune Cell Phenotyping		X ^a		X	X		X ^a		X	X		X ^a	X	X ^a	X	X ^p		
Blood Sample for Cytokines		X ^a	X	X	X		X ^a	X	X	X		X ^a	X	X ^a	X	X ^p		
Blood Sample for Anti-HLA Antibody		X ^a					X ^a					X ^a		X ^a		X		
IRT Transaction Required	X	X ^m					X					X		X		X		
ASP7517 Dosing at the Clinic		X ⁿ					X ⁿ					X ⁿ		X ⁿ				X
Survival Follow-up ^q																		

AE: adverse event; CT: computed tomography; C: cycle; C1D1: cycle 1 day 1; CR: complete remission; D: day; ECG: electrocardiogram; ECHO: echocardiogram; ECOG: Eastern Cooperative Oncology Group; ELISpot: enzyme-linked immunospot; EoT: end-of-treatment; HLA: human leukocyte antigen; ICF: informed consent form; INR: international normalization ratio; IP: investigational product; IRT: interactive response technology; MUGA: multigated acquisition scan; PGx: pharmacogenomics; PT: prothrombin time; SAE: serious adverse event; WOCBP: women of childbearing potential; WT1: Wilms' tumor 1 protein.

- Obtained predose.
- Obtained predose and postdose (vital signs: hourly [\pm 10 minute window] for up to 4 hours postdose; ECG: 1 to 2 hours postdose) on day 1 of each cycle.
- Height measurement performed only at screening. Weight measurement should be performed at screening and day 1 of each cycle.
- Includes medications taken within 28 days prior to C1D1.

Footnotes continued on next page

- e. WOCBP must have a negative serum or urine pregnancy test (minimum sensitivity 25 IU/L or equivalent units of human chorionic gonadotropin) within 72 hours prior to the start of study treatment.
- f. The 12-lead ECGs will be recorded in triplicate (at least 2 minutes apart per time point) and transmitted electronically for central reading.
- g. Laboratory samples will be analyzed by the institution's local laboratory. However, sample results must also be submitted for centralized data entry. Laboratory tests and/or ECG can be repeated during screening period. Laboratory samples will be analyzed by the institution's local laboratory and results will be submitted for centralized data entry.
- h. Chest X-ray (or CT of chest) does not need to be repeated if performed within 2 weeks prior to start of screening.
- i. MUGA scans or ECHO (per standard of care) performed at screening or within 28 days prior to screening will be accepted.
- j. Screening samples may be collected up to 28 days prior to C1D1. End of treatment bone marrow sample does not need to be repeated if collected within 2 weeks of the last disease assessment. Samples must be submitted to a central laboratory for analysis. If bone marrow aspirate is unobtainable (e.g., dry tap), an additional ethylenediaminetetraacetic acid tube of whole blood should be collected instead. Bone marrow aspirate is required, and bone marrow biopsy is preferred. In case of inadequate aspirate, bone marrow biopsy is required.
- k. Samples must be submitted to a central laboratory for analysis. If a participant achieves CR at any point during the treatment period and ASP7517 is not continued, an EoT visit should be performed and the participant should proceed to observation period 1.
- l. Whole blood and buccal swab for optional PGx study may be collected at C1D1 prior to first investigational product administration.
- m. Subject enrollment in the study will be conducted via IRT transaction.
- n. After dosing of ASP7517, subjects must be observed for safety for a minimum 4 hours. The safety observation will consist of vital signs and AE observations. If new AEs are observed that are \geq grade 3 during this time, subjects should continue to be observed at the investigator's discretion.
- o. The EoT visit will occur within 7 days of the principal investigator decision to discontinue the subject for treatment or prior to the initiation of a new anticancer treatment, whichever occurs first. If a subject is completing all visits in the last treatment cycle, the EoT visit will be within 7 days from the last planned visit.
- p. Assessment does not need to be repeated if collected at a regularly scheduled visit within 3 days of EoT visit.
- q. Telephone contact for survival status and subsequent anti-cancer treatments and outcomes.
- r. After the first 2 cycles of treatment, subjects who have not met any individual treatment discontinuation criteria and are receiving clinical benefit (defined as achieve CRc or PR for AML and CR, BM CR or PR or HI for MDS or other clinical benefits, as determined by the investigator) will continue further treatment of ASP7517 as decided by the investigator.
